8.6 Treatment Compliance

Study treatment must be dispensed or administered according to procedures described herein. Only participants enrolled in the study may receive study treatment. Only authorized site personnel may supply study treatment. Participants will record use of the study medication utilizing the study diary at the time of use each day. Participants will review study medication compliance with the Investigator or designee. Any missed doses, timing, and reason for missed dose will be recorded in the eCRF. There should be no doubling of doses to make up for missed doses. If a dose is missed, the next dose of study medication should be taken as scheduled.

Each site participating in the trial will be instructed to assess subject's compliance by weighing the investigational product at the Baseline visit, Week 2 visit, and Week 4 visit and followed every time study medication is dispensed and returned per instructions below. Sites will be provided scales, which will be calibrated prior to each use. Study personnel will be instructed to record measurements into the eCRF.

All weight measurements will be performed without the safety cap. Subjects will be dispensed 2 bottles upon randomization, and each bottle will be labeled 1 and 2 with a permanent marker at the site. Unused Bottle 1 will be vortexed, primed, and weighed without the cap by the site per treatment application instructions and dispensed to the subject who will mix and apply the first dose at the site under study staff supervision. Bottle 2 will also be vortexed, primed, and weighed at the site at the time of dispense without the cap, the cap inserted back on the bottle,

and the bottle returned to its carton unused. After the first treatment application of Bottle 1, subjects will take home both bottles where they will place Bottle 1 on the counter at room temperature for in-home application twice a day until empty. Bottle 2 will be stored in the refrigerator until Bottle 1 is empty, at which point Bottle 2 will be taken out of the refrigerator, mixed per treatment application instructions, and used. Should Bottle 1 run out during a treatment application, the subject will count the number of pumps that were made with Bottle 1 and complete the remaining number of pumps needed to achieve a total of 10 pumps using Bottle 2.

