At the Week 2 visit, subjects will return any empty bottle (likely Bottle 1 since each bottle should last approximately 10 days and the subject should be on Bottle 2 at the time of visit) to the site for weight measurement (without the safety cap) to confirm usage. At this visit, a third bottle of the same treatment group will be labeled as Bottle 3 and will be vortexed, primed, and weighed at the site at the time of dispense without the cap, the cap inserted back on the bottle, and the bottle returned to its carton unused. The subject will be dispensed Bottle 3 to take home and store in the refrigerator until Bottle 2 is empty, at which point Bottle 3 is taken out of the refrigerator and used on the counter until the Week 4 visit. All empty bottles returned to the site will be collected and stored by the site in ambient temperature until return to the drug depot. If the subject is still on Bottle 1 at the Week 2 visit, the site will confirm daily dosing application and retrain the subject on the appropriate use of IP application, and the subject will continue using Bottle 1 until empty, at which point Bottle 2 is taken out of the refrigerator and used on the counter until Bottle 2 is empty, after which Bottle 3 is taken out of the refrigerator and used on the counter until the Week 4 visit. Any bottle currently in use at the time of the Week 2 visit should not be returned to the site.

At the Week 4 visit, all used and unused bottles will be returned to the site for weight measurements and storage at the site in ambient temperature until return to the drug depot.

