7.2.5 Per-Protocol (PP) Population

The PP population includes all subjects in the mITT population without any major protocol deviations that may have an impact on the efficacy assessments, who complete their Week 4 visit, and who administer at least 50% of investigational product (IP). Subjects will be grouped as treated.

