7.2.6 Role of Populations in Analyses

The results in the mITT population will be considered definitive for superiority of each active treatment to vehicle with those in the PP population considered supportive. Safety analyses will be performed using the Safety population.

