7.5.1 Study Drug Exposure

Subject dosing/exposure is recorded in both the ERT (patient diary entries) and EDC (site entries). In case of any discrepancies of the first and/or last exposure date between ERT and EDC, the EDC date will be used. Only ERT records that fall within the first and last dosing dates reported in the EDC (inclusive) will be retained.

Each site participating in the trial will be instructed to assess subject's compliance by weighing the investigational product at the Baseline visit, Week 2 visit, and Week 4 visit and followed every time study medication is dispensed and returned.

At the Week 2 visit, subjects will return any empty bottle (likely Bottle 1 since each bottle should last approximately 10 days and the subject should be on Bottle 2 at the time of visit) to

STATISTICAL ANALYSIS PLAN

Version 3.0 12-Jan-22

the site for weight measurement. At the Week 4 visit, all used and unused bottles will be returned to the site for weight measurements.

The cumulative amount of study drug exposure will be estimated by calculating the difference between the weight of all bottles of drug dispensed and the weight of all bottles returned. Differences will be summed together and reported as Net Weight of Study Drug.

The amount of product used per day will be estimated by dividing the change by the number of days the subject was on treatment. These weights will be compared to the weight of the product that would be used if the subject was compliant with the protocol. Percent compliance will be calculated as follows, with planned study drug use per day defined as 2.8g (0.14 g per pump x 10 pumps per application x 2 applications per day = 2.8 g) and number of days = 28 days:

Percent compliance = $\frac{\text{Net Weight of Study Drug}}{[Planned study drug use per day] * Numbers of days} \times 100$

The expected amount of study drug used over 4 weeks is approximately 0.14 g per pump x 10 pumps per application x 2 applications per day x 28 days of treatment = 78.4 g. The compliance will be calculated for Baseline to Week 4 visit.

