The total dispensed and returned IP weights, the Net Weight of Study Drug, and the percent compliance during the treatment period will be summarized by treatment group and pooled B244 treatment and will be presented in a by-subject data listing. Percent compliance will be calculated for all subjects who received study drug, even if they did not return any/all of their study drug kits. Kits not returned will be assumed to be fully used and the return weight will be imputed as 0g. In the listing, the total weight dispensed, returned, net weight, and % compliance will be presented.

Dose compliance for each subject will also be calculated based on the number of daily study drug dosing diaries entered out of the total study drug dosing diaries available (2 study drug dosing diaries available per day x 28 days of treatment = 56 available entries). Only ERT dosing diary records from date of first dose through date of Visit 4-1 will be considered for calculating secondary compliance.

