| Investigator's Decision | n (%) | xx (xx.x) | xx (xx.x) | xx (xx.x) | xx (xx.x) | xx (xx.x) |
| Adverse Event | n (%) | xx (xx.x) | xx (xx.x) | xx (xx.x) | xx (xx.x) | xx (xx.x) |
| Pregnancy | n (%) | xx (xx.x) | xx (xx.x) | xx (xx.x) | xx (xx.x) | xx (xx.x) |
| Significant Non-Compliance | n (%) | xx (xx.x) | xx (xx.x) | xx (xx.x) | xx (xx.x) | xx (xx.x) |
| Significant Clinical Event | n (%) | xx (xx.x) | xx (xx.x) | xx (xx.x) | xx (xx.x) | xx (xx.x) |
| Incident of Unblinding | n (%) | xx (xx.x) | xx (xx.x) | xx (xx.x) | xx (xx.x) | xx (xx.x) |
| Failure to Meet Continuation Criteria | n (%) | xx (xx.x) | xx (xx.x) | xx (xx.x) | xx (xx.x) | xx (xx.x) |
| Other | n (%) | xx (xx.x) | xx (xx.x) | xx (xx.x) | xx (xx.x) | xx (xx.x) |

Table 14.1.1.1 Subject Enrollment and Disposition (All Subjects)

[1] Percentage based on the number screened.

[2] The number enrolled is equal to the sum of the number randomized and the number not assigned.

[3] Not Assigned includes subjects who passed the initial inclusion/exclusion assessment, but withdrew or were lost-to-follow-up prior to randomization.

[4] Percentage based on the number enrolled.

[5] Percentage based on the number randomized.

[6] Percentage and all subsequent percentages based on the number treated.

[7] Completed the Study indicates completion up to and including Week 8 visit.

[8] Safety Population: All subjects treated with at least 1 dose of IP.Modified Intent-to-Treat Population: All randomized participants who apply at least 1 dose of IP and have at least one post-baseline evaluation visit.

Per Protocol Population: Includes all subjects in the mITT population who administered at least 50% of IP (based on the weight of IP used calculated using the algorithm: difference in weight of all bottles dispenced and weight of all bottles returned must be at least 50% of the initial theoretical product weight i.e.(0.14 g per pump x 20 pumps per day x 28 days = 78.4 g)), have completed their Week 4 visit and did not have any major protocol deviations. Source: Listing XXXX

PROGRAM NAME: XXXXXXXXXX

DATE: HH:MM/DDMMMYYYY

Programming Note:

• Reason for Early Study Discontinuation response "Significant Clinical Event" corresponds to the CRF response "Any clinical AE, lab abnormality, or other medical condition or situation occurs such that continued participation in the study would not be in the best interest of the subject."

Table 14.1.1.2 Analysis Populations and Exclusions (All Enrolled Subjects)

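### Imputing 0 g for an unreturned bottle counts the empty container as drug in net weight, percent compliance and the 50% per-protocol check

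*SAP*

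**What the plan says.** SAP 7.5.1 estimates cumulative exposure by "calculating the difference between the weight of all bottles of drug dispensed and the weight of all bottles returned" and calls the result Net Weight of Study Drug. Percent compliance divides it by planned use: 2.8 g per day for 28 days, or 78.4 g. For bottles that do not come back, the rule is "Kits not returned will be assumed to be fully used and the return weight will be imputed as 0g".

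Protocol 8.6 describes the weighing. Each bottle is weighed with its contents when dispensed, and the convention throughout is "All weight measurements will be performed without the safety cap". At Week 2, empty bottles go back "to the site for weight measurement (without the safety cap) to confirm usage". All remaining bottles are weighed at Week 4. Neither document subtracts a container weight or mentions taring.

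Net weight also decides entry to the per-protocol (PP) set. The footnotes to SAP Tables 14.1.1.1 and 14.1.1.2 require that the "difference in weight of all bottles dispenced and weight of all bottles returned must be at least 50% of the initial theoretical product weight", with 78.4 g as the base. Table 14.3.5 and Listing 16.2.5.2 carry the same 50% flag. SAP 7.2.6 treats mITT results as definitive, "with those in the PP population considered supportive".

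**The concern.** The two halves of the imputation rule do not agree. On the scale described in the protocol, a fully used bottle weighs what an empty bottle weighs, not 0 g. When a bottle is returned, its container appears in both weights and cancels. When it is not returned and 0 g is imputed, the container stays in the numerator, while the 78.4 g denominator is drug only. The error is always upward.

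This is distinct from the full-use assumption. That is a declared choice and inflates compliance in its own right; the point here is only the extra container weight, which full use does not justify.

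At stake are the exposure and compliance summaries in the Safety population, the by-subject listing, and PP membership for a subject with one missing bottle and little measured use from the others.

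**Working it through.** **Inputs from the documents.** 0.14 g per pump, 10 pumps per application, 2 applications per day, 28 days (SAP 7.5.1). 30 ml bottles, each expected to last about 10 days; two dispensed at Baseline and one at Week 2 (Protocol 8.6 and 8.15).

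**Assumptions, not in the documents.** Empty weight T = 5, 10 or 20 g. Fill F = 30 g (30 ml at 1 g/ml) or 28 g (10 days × 2.8 g).

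**The plan's own figure.** 0.14 × 10 × 2 = 2.8 g per day; 2.8 × 28 = 78.4 g. This reproduces. The 50% threshold is 39.2 g.

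**Effect of one unreturned bottle.**
- As written: (F + T) − 0 = F + T.
- With the empty weight imputed: (F + T) − T = F.
- Excess: T grams, or 100 × T / 78.4 percentage points.

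| T (g) | Excess per bottle (points) | Full complier, third bottle unreturned, F = 30 | Same, F = 28 |
|---|---|---|---|
| 5 | 6.4 | 95/78.4 = 121% | 89/78.4 = 114% |
| 10 | 12.8 | 100/78.4 = 128% | 94/78.4 = 120% |
| 20 | 25.5 | 110/78.4 = 140% | 104/78.4 = 133% |
| Empty weight imputed | 0 | 90/78.4 = 115% | 84/78.4 = 107% |

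The excess over 100% in the last row is the full-use assumption alone.

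**Early loss.** A subject in the Safety population who returns neither Baseline bottle is reported at (60 + 2 × 10)/78.4 = 102% with F = 30 and T = 10, against 60/78.4 = 77% with the empty weight.

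**PP check, one bottle unreturned.** Let X be measured use from the other bottles.
- Empty weight imputed: the subject passes if X ≥ 39.2 − F, that is 9.2 g (F = 30) or 11.2 g (F = 28).
- As written: the subject passes if X ≥ 39.2 − F − T. At T = 5 this is 4.2 g or 6.2 g.
- The required X falls to zero once T reaches 9.2 g (F = 30) or 11.2 g (F = 28).

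**PP check, two bottles unreturned.** Contents alone give 56/78.4 = 71% or 60/78.4 = 77%. The subject passes whatever T is, so the container weight changes nothing here.

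**Group mean.** The non-return rate is not given. If 2% to 10% of subjects miss one bottle and T = 10 g, mean compliance rises by 12.76 × 0.02 = 0.3 to 12.76 × 0.10 = 1.3 points.

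**The case against.** The best counter-argument is that the weighing may have been net. The schedule of events refers to separate instructions given to sites, and these are not in the documents. SAP 7.5.1 also speaks of IP weights. If scales were tared to an empty bottle, 0 g would be exactly right for a fully used kit. This cannot be excluded, but the available text points to gross weighing: the only part removed is the cap, and empty bottles are weighed to confirm use.

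The second argument is that the consequences are small, and much of it stands. T is assumed, so the documents fix the direction of the error but not its size. PP status changes only for a subject with exactly one missing bottle, a completed Week 4 visit, no major deviation affecting efficacy, and less than 9.2 to 11.2 g used from the other two bottles, out of roughly 56 to 60 g. That describes a grossly non-adherent subject, and such subjects are likely to be few. The SAP sets no upper compliance limit, so a figure of 128% triggers nothing.

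The plan also tabulates a diary-based compliance measure and lists weights by kit, so the effect can be traced. Neither corrects the 50% flag or the reported compliance.

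**Conclusion.** The concern holds. On the weighing procedure the protocol describes, 0 g contradicts the assumption of full use and overstates net weight by one container per unreturned bottle. This rests on the weights being gross, which the text supports but the unseen site instructions could overturn.

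For an individual subject the error could be large: 6 to 26 points per bottle over the assumed range of T. For group means it is probably about a point or less, and for PP membership it probably concerns isolated subjects. The mITT primary analysis does not use these weights. The change is worth making because the rule is wrong as written and easy to correct; it does not threaten the trial's main conclusion.

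**What to change.** In SAP 7.5.1, replace the 0 g return weight with the mean weight of returned empty bottles, and use it for Net Weight, percent compliance and the 50% PP rule. Week 2 returns are a direct source, because Protocol 8.6 says: "Any bottle currently in use at the time of the Week 2 visit should not be returned to the site". Bottles handed back then should be empties. First confirm from the site instructions that weights are gross; if they were tared, keep 0 g and state the reason.

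The cost is one wording change and a small derivation change using weights already recorded by kit. A few borderline subjects may leave the PP set.

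Optionally, to address the separate full-use assumption, show compliance and PP membership with subjects who have any unreturned bottle (a) excluded, and (b) classified by the existing dosing-diary count, at least 28 of 56 entries. Under (b), membership can move either way. The correction does not depend on these analyses.

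### Unreturned kits are scored as fully used, so the 50% per-protocol dose check cannot fail for a subject who keeps two or more bottles

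*SAP*

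**What the plan says.** SAP 7.5.1 estimates cumulative exposure as "the difference between the weight of all bottles of drug dispensed and the weight of all bottles returned" and divides it by a planned use of 78.4 g to get percent compliance. It covers everyone who was treated: "Percent compliance will be calculated for all subjects who received study drug, even if they did not return any/all of their study drug kits". For a bottle that does not come back, the rule is: "Kits not returned will be assumed to be fully used and the return weight will be imputed as 0g".

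SAP 7.2.5 admits to the PP set mITT subjects who complete the Week 4 visit, have no major deviation bearing on efficacy, and used at least half of the product. The footnotes to Tables 14.1.1.1 and 14.1.1.2 make the last condition operational: "difference in weight of all bottles dispenced and weight of all bottles returned must be at least 50% of the initial theoretical product weight", that weight being 78.4 g. Table 14.3.5, footnote 3, defines its 50% IP Applied row on the same net weight. The imputation therefore feeds both the PP criterion and the compliance summary.

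The SAP also derives a measure that needs no bottles: "Dose compliance for each subject will also be calculated based on the number of daily study drug dosing diaries entered", out of 56 possible entries. PP membership does not use it. The SAP gives no cap, exception or sensitivity analysis for imputed weights, and SAP 7.6 does not list this imputation among its missing-data rules.

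**The concern.** The dose criterion is there to remove subjects who used too little product. For an unreturned bottle, its input is the weight handed out, which carries no information on use. The imputed value is the largest possible, so the error runs only towards higher compliance, and it arises exactly where adherence is unknown.

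Two outputs are exposed. The PP set, meant to contain adherent subjects, can include someone who attended Week 4, sprayed very little and left the bottles at home. And Table 14.3.5 can report a subject lost in the first days as well above half compliant, raising the arm's mean.

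**Working it through.** **Inputs**
- Use per pump, pumps, applications and days: SAP 7.5.1.
- Bottle size 30 ml: Protocol 8.1. Two bottles are dispensed at Baseline and a third at Week 2: Protocol 8.6.
- Weighing after priming and without the safety cap, with no subtraction of the container stated: Protocol 8.6.
- Contents per bottle in grams: not stated. Assumed 30 g (30 ml at 1 g/ml), with a range of 27 to 31 g.

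**The plan's own figure.** 0.14 × 10 × 2 = 2.8 g per day, and 2.8 × 28 = 78.4 g. This reproduces SAP 7.5.1. Threshold: 0.5 × 78.4 = 39.2 g.

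**Check on the 30 g assumption.** 30 / 2.8 = 10.7 days per bottle, against about 10 days in Protocol 8.6 and SAP 7.5.1. The assumption is plausible.

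**Score from the imputation alone** = (unreturned bottles × contents) / 78.4

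| Unreturned bottles | At 30 g each | At 27 to 31 g each | Passes 50%? |
|---|---|---|---|
| 1 | 30 / 78.4 = 38.3% | 34.4% to 39.5% | Not alone |
| 2 | 60 / 78.4 = 76.5% | 68.9% to 79.1% | Always |
| 3 | 90 / 78.4 = 114.8% | 103.3% to 118.6% | Always |

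- With two unreturned and the third returned, the score lies between 76.5% (third returned full) and 114.8% (third returned empty).
- Two unreturned bottles pass whenever each was recorded at 39.2 / 2 = 19.6 g or more, so the pass does not hinge on exactly 30 g.
- With one unreturned bottle, the subject needs 39.2 − 30 = 9.2 g from the others, or 9.2 / 2.8 = 3.3 days of use.

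**If recorded weights include the container.** For a returned bottle the container cancels in the difference. For an unreturned one it is counted as drug. With an assumed container of 5 to 20 g, two unreturned bottles score 2 × 35 / 78.4 = 89% to 2 × 50 / 78.4 = 128%, and three score 134% to 191%. One unreturned bottle passes alone once the container weighs 9.2 g.

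**Illustrations**
- Week 4 attendee with one application (1.4 g, true use 1.4 / 78.4 = 1.8%) and no bottle returned: scored 114.8%, dose criterion met.
- Subject lost after five days with both baseline bottles: true use 5 × 2.8 = 14 g, or 14 / 78.4 = 17.9%; reported as 76.5% with 50% IP Applied met. This affects Table 14.3.5 only, because the Week 4 visit is missing.

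**Would dropping non-returners correct the mean?** Let a share p of subjects be non-returners with true use 17.9%, and let R be the mean among returners. The current rule overstates the overall mean by p × (76.5 − 17.9). Dropping them overstates it by p × (R − 17.9), which is worse whenever R exceeds 76.5%. With p = 10% and R = 90%, both assumed only for illustration, the errors are 5.9 and 7.2 points.

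**The case against.** Several points on the other side stand.

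- **Reach into the PP set is narrow.** A reader might infer that early dropouts who keep their bottles enter the PP set. They do not: SAP 7.2.5 also requires the Week 4 visit and no relevant major deviation.
- **Site procedures narrow it further.** Under Protocol 8.6, empty bottles come back at Week 2, a subject still on Bottle 1 then is retrained, and all bottles are due at Week 4. A subject who returned Bottle 1 empty has already used about 30 g (38%).
- **Another exclusion route exists.** Deviations are graded before unblinding under a separate guidance document (SAP 7.3.2), and Protocol 12.7 lists deviations in product administration. That guidance is not among the documents, so it cannot be judged whether it would catch under-dosing or unreturned kits.
- **The imputation is visible.** Table 14.3.5 shows diary compliance beside weight compliance, and Listings 16.2.5.1 and 16.2.5.3 give the detail by subject.
- **Non-return need not mean non-use.** A discarded empty bottle was fully used, and for its contents the rule is then right.
- **The consequence is limited.** SAP 7.2.6 makes mITT definitive and PP supportive, and including low users would tend to dilute a superiority comparison rather than flatter it.

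These points limit the size of the problem but do not remove it. Nothing in the documents stops the check from passing a subject with two unreturned bottles, and showing both compliance measures does not change who is in the PP set.

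**Conclusion.** The point holds in limited form and should be corrected. For a subject who fails to return two or more bottles, the 50% criterion gives the same answer whatever was applied. The scores of 77% and 115% assume about 30 g of contents per bottle; the pass itself needs only 19.6 g per bottle. If weights include the container, the scores are higher.

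The PP effect is confined to Week 4 completers without a major deviation who lack at least two bottles. Table 14.3.5 is affected by any non-returner.

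Two stronger readings are not supported. The primary mITT analysis does not depend on this derivation. And no particular inflation of mean compliance, overall or in one arm, can be claimed, because the documents give no non-return rate.

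**What to change.** - **PP criterion.** In SAP 7.5.1 and the PP footnotes of Tables 14.1.1.1 and 14.1.1.2, decide the 50% criterion on the dosing diary for any subject with an unreturned kit: at least 28 of 56 doses confirmed. At minimum, repeat the PP analysis without subjects whose 50% status depends on an imputed weight. If the PP set is already fixed, this can be added as a sensitivity analysis.
- **Table 14.3.5.** Give the number of subjects with unreturned kits per arm. Show weight-based compliance separately for subjects with all kits returned and for those with imputed weights, labelling the latter an upper bound, and put diary compliance next to both. Do not simply drop non-returners from the mean: as shown above, that can overstate compliance more than the current rule does.

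**Cost.** SAP wording, a few lines of derivation and extra table rows; no new data. The diary is self-reported, counts a missing entry as a missed dose, and records doses rather than amount. The criterion would then rest on two data sources, and some non-returners would leave the PP set.
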